3.4.3. Clinical Laboratory Results

Laboratory data will be listed by subject. Values above and below normal ranges will be indicated. All laboratory values will be graded according to the NCI-CTCAE version 4.03 criteria. Laboratory data will be summarized by actual value and change from baseline using number of non-missing observations, mean, standard deviation, median, minimum, maximum, and Grade 3 and 4 by dose cohort and by disease cohort treated at RP2D and schedule. In addition, shift tables will be presented.

3.4.4. Vital Signs

Vital signs will be listed by subject. Vital sign data will be summarized by actual value and change from baseline using number of non-missing observations, mean, standard deviation, median, minimum and maximum by dose cohort for Phase 1 subjects and by MDS/CMMML disease cohort for Phase 2a subjects treated at RP2D and schedule.

3.4.5. Physical/Other Examinations

Data collected for physical examinations, ECGs and related measures will be listed. ECGs change from baseline will be summarized by dose cohort for Phase 1 subjects and by MDS/CMMML disease cohort for Phase 2a subjects.

3.4.6. Treatment Discontinuation, Project Termination, and Death

The participants who discontinued (with reasons) and deaths will be listed. The treatment emergent adverse events leading to permanent discontinuation from study will be presented.

4. Proposed Summary Tables, Graphs and Listings

4.1. Mock Tables

The following tables will be presented by dose cohort for subjects in Phase 1 dose escalation phase, and by disease cohort for subjects in Phase 2a.

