The primary endpoint will be the proportion of subjects who achieve an objective response (OR) as best response (CR, CRi or PR). Each dose cohort will be analyzed independently. For the primary efficacy endpoint, OR by disease type (AML, MDS, CMML) will be summarized using the number and percentage of subjects with an OR. The proportion of subjects with hematologic improvement in peripheral blood or bone marrow blast count and 90% confidence intervals will be estimated. For secondary endpoints, PFS and OS, curves will be estimated for each dose cohort and disease type using Kaplan-Meier product-limit estimates.	
Pharmacokinetic and Pharmacodynamic Endpoint Analyses: Analysis plans will be described in the written plans provided by the laboratories performing the analyses.	

TABLE OF CONTENTS

INVESTIGATOR SIGNATURE PAGE	2
SYNOPSIS	3
LIST OF FIGURES	12
LIST OF APPENDICES	12
LIST OF ABBREVIATIONS	13
1. INTRODUCTION	15
1.1. FF-10501-01 Background.....	15
1.2. SM-108 Preclinical Summary.....	15
1.3. SM-108 Previous Human Experience.....	16
1.3.1. Phase 1 Study in Advanced Solid Tumors or Hematologic Malignancies	16
1.3.2. Phase 2 Study in Advanced Lung Cancer.....	16
1.3.3. Phase 2 Study in Advanced Hematologic Malignancies	17
1.4. FF-10501-01 Preclinical Pharmacology	18
1.4.1. Induction of differentiation in myeloid leukemia cell lines.....	18
1.4.2. In Vitro Growth Inhibition in Myeloid Leukemia Cell Lines.....	19
1.4.3. Inhibition of Growth in an Azacitidine-resistant Cell Line	20
1.4.4. FF10501-01 Mechanism of Action.....	20
1.4.5. Anti-tumor Activity in a Human Myeloid Leukemia SKM-1 Xenograft Model in Mice	21
1.5. FF-10501-01 Preclinical Pharmacokinetic, Metabolism, Excretion.....	22
1.5.1. Single Oral Dose Pharmacokinetics.....	22
1.5.2. Multiple Dose Oral Pharmacokinetics	22
1.5.3. Distribution	23
1.5.4. Metabolism	23
1.5.5. Excretion	23
1.6. Toxicology	24
1.6.1. Repeat-dose Toxicity Studies in Rats	24
1.6.2. Repeat-dose Toxicity Studies in Dogs.....	24
1.6.3. Genotoxicity.....	25
1.6.4. Phototoxicity	25
1.7. FF-10501-01 Experience in Humans	25
1.7.1. Japan Phase 1 Study.....	25
1.7.2. U.S. Phase 1/2a Study	26
1.8. Dose Rationale.....	27
2. STUDY OBJECTIVES	27
2.1. Primary Objective:	27
2.2. Secondary Objective:	27
3. INVESTIGATIONAL PLAN	28
3.1. Overall Study Design.....	28
3.2. Number of Subjects and Centers.....	30
3.3. Duration of Study.....	30
3.4. Criteria for Termination of the Study	30
4. STUDY POPULATION	31
4.1. Inclusion Criteria	31

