8.3.2.2. Secondary Efficacy Endpoints

The proportion of MDS subjects with hematologic improvement in the peripheral blood or bone marrow as defined as $\geq 50\%$ reduction in blast count when compared with the baseline value. The 90% confidence interval will be estimated and provided.

Progression-free survival and overall survival curves will be estimated at the MTD by disease cohort using Kaplan-Meier product limit estimates. Median and 90% confidence interval of time-to-event will be estimated. Progression-free survival will be calculated from the date of first dose of study drug to the date of first objective evidence of disease progression or death, whichever is earlier. Overall survival will be calculated from the date of first dose of study drug to the date of death due to any cause. Subjects who did not experience progression or death will be censored at the last follow-up time point.

8.3.3. *Pharmacokinetic Endpoint Analysis*

Mean plasma concentrations of FF-10501 and plasma M1 will be determined at each time point for evaluation of dose-linearity. Because a limited number of plasma concentrations will be determined, full determination of routine pharmacokinetic parameters may not be possible. In addition to mean plasma concentrations, as the data allow, additional pharmacokinetic analyses will be provided (trough levels, $t_{1/2}$, T_{max} , C_{max} , AUC, etc.)

8.3.4. *Pharmacodynamic Endpoint Analysis*

Change from baseline in XMP levels will be measured in blood samples collected from each subject during the study. Correlations between XMP and PK levels of FF-10501 will be made. Pharmacodynamic parameters will be summarized using descriptive statistics

including the number of subjects, mean, standard deviation, minimum, median, maximum, range, and coefficient of variation.

8.3.5. *Other Summaries*

Demographics and concomitant medications, including antibiotic usage, will be summarized using descriptive statistics. Medical history findings and protocol deviations will be listed but not summarized.

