3.3. Analysis of Efficacy

All efficacy analyses will be conducted for Phase 1 subjects by dose cohort, if applicable, and for Phase 2a subjects by MDS/CMMML disease cohort at the RP2D and schedule (400 mg/m² BID x 21 days, repeated every 28 days) using the Per Protocol Population (PPS dataset).

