4.1.5. Secondary Efficacy Summaries

- Summary of Subjects With Hematologic Improvement
- Progression Free Survival (PFS)
- Overall Survival (OS)

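### The SAP groups Phase 1 PFS and OS by dose cohort only, dropping the protocol's disease-specific curves at the MTD and leaving no planned AML PFS or OS estimate in the text available

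*SAP*

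**What the plan says.** The protocol asks for a disease split in two places, though not the same one.

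- Protocol 8.3.2.2: "Progression-free survival and overall survival curves will be estimated at the MTD by disease cohort using Kaplan-Meier product limit estimates". The next sentence adds: "Median and 90% confidence interval of time-to-event will be estimated".
- Protocol synopsis, efficacy analyses: for PFS and OS, "curves will be estimated for each dose cohort and disease type using Kaplan-Meier product-limit estimates". It does not restrict this to the MTD, and it mentions no median or interval for these endpoints.

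The SAP uses another grouping.

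- SAP 3.3: "All efficacy analyses will be conducted for Phase 1 subjects by dose cohort, if applicable, and for Phase 2a subjects by MDS/CMMML disease cohort", the latter at the RP2D and schedule.
- SAP 4.1 has the tables "presented by dose cohort for subjects in Phase 1 dose escalation phase, and by disease cohort for subjects in Phase 2a".
- SAP 3.3.2 defines PFS and OS but adds no grouping, estimator or interval.
- SAP 4.1.4 lists one response table for AML and another for MDS/CMML. SAP 4.1.5 lists a single PFS table and a single OS table, and SAP 4.2 a single graph for each.

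Protocol 3.1 limits AML to Phase 1 and makes Phase 2a an MDS/CMML cohort of 20. Phase 1 subjects at the RP2D and schedule who meet the Phase 2a criteria count toward those 20.

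**The concern.** PFS and OS are stated secondary objectives in both documents. The SAP's only disease split for them sits in Phase 2a, which AML subjects cannot enter. Followed as written, the SAP gives the largest disease group in the trial no curve of its own, although 8.3.2.2 promises one at the MTD.

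The curves it does plan for Phase 1 can combine diseases. For PFS this is a matter of definition. Protocol 7.2.2.1 gives AML a treatment-failure category and a recurrence category. Protocol 7.2.2.2 defines progressive disease for MDS/CMML through failure to reach PR, CR or marrow CR, and adds separate relapse rules. The timing of a PFS event in a mixed cohort would then depend partly on which diseases happened to be enrolled. OS has one event definition, so mixing there affects prognosis and interpretation but not what counts as an event.

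**Working it through.** **1. The plan's own totals.** SAP 2.1 gives 3 to 6 subjects in up to 8 cohorts: 8 × 6 = 48. Adding Phase 2a: 48 + 20 = 68. Both agree with the SAP.

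**2. The groupings side by side.**

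| Source | Phase 1 grouping for PFS/OS | AML curve planned? |
|---|---|---|
| Protocol 8.3.2.2 | Disease, subjects at the MTD | Yes, at the MTD |
| Protocol synopsis | Dose cohort and disease type | Yes, but unclear whether within each dose cohort or across doses |
| SAP 3.3, 4.1, 4.1.5, 4.2 | Dose cohort | No |

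**3. Who is affected relative to 8.3.2.2.** Inputs from protocol 1.7.2: 33 treated to date, 25 AML and 8 MDS (25/33 = 76% AML), and 7 treated at 400 mg/m² BID × 14 days. Protocol 3.1 says the 14-day cohorts had 3 subjects each before the 400 mg/m² cohort was expanded. The final sizes of the other five cohorts (50, 100, 200, 300 and 500 mg/m²) are not otherwise given, so I assume 3 each.

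- Outside 400 mg/m²: 5 × 3 = 15.
- At 400 mg/m²: 33 − 15 = 18, of whom 7 are on 14 days and 18 − 7 = 11 are in Cohorts 7 and 8. The split of the 11 is not given.
- Fewest AML at 400 mg/m²: all 15 others have AML, so 25 − 15 = 10.
- Most AML at 400 mg/m²: all 18. Protocol 1.7.2 reports an MDS responder at 400 mg/m² × 14 days, so the attainable maximum is 17.
- Proportional allocation: 18 × 25/33 = 13.6, about 14.

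Each further subject in one of the other five cohorts lowers both counting bounds (10 and 18) by one. The MDS subjects at 400 mg/m² are the complement, at most 18 − 10 = 8. The MDS responder on the 14-day schedule was not on the 21-day RP2D schedule, so at least one such subject falls outside Phase 2a.

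**4. How likely a dose cohort is to mix diseases.** Assume the 25 AML and 8 MDS subjects fall into cohorts at random. Then P(mixed) = 1 − [C(25,n) + C(8,n)]/C(33,n).

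- n = 3: 1 − (2300 + 56)/5456 = 0.57.
- n = 7: 1 − (480700 + 8)/4272048 = 0.89.

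**5. What the 8.3.2.2 grouping offers in precision.** As a guide, take the exact (Clopper-Pearson) 90% interval for the proportion surviving to a fixed time, near 50%, with no censoring.

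| n | Events | 90% interval | Width |
|---|---|---|---|
| 3 | 1 | 0.017 to 0.865 | 0.85 |
| 7 | 3 | 0.129 to 0.775 | 0.65 |
| 10 | 5 | 0.222 to 0.778 | 0.56 |
| 18 | 9 | 0.291 to 0.709 | 0.42 |

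A by-disease AML curve at the MTD would still be imprecise, but more informative than a small dose cohort and specific to one disease. This assumes the three schedules at 400 mg/m² are pooled.

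**The case against.** The strongest reply is that the gap is narrower than it may look. Several stronger readings should be set aside.

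- **That 25 AML subjects lose a planned estimate.** A reader might infer this from 25 of 33. But 8.3.2.2 plans disease curves only at the MTD, so AML subjects at other doses have no AML curve there either. The synopsis might be read as planning an all-dose AML curve, but if disease is crossed with dose cohort its cells are smaller than the SAP's. No text clearly plans a 25-subject curve.
- **That a planned 90% interval for the median is unattainable in 3-subject cohorts.** The widest order-statistic interval covers 1 − 2 × 0.5³ = 75% at n = 3. But the median and 90% interval are stated only for the MTD-by-disease grouping. No visible text asks for them in a 3-subject dose cohort, and no interval method is named.
- **That the Phase 1 curves hold 3 to 7 subjects.** The sizes of Cohorts 7 and 8 are not given. One could hold up to 11 on the allocation above, or the 400 mg/m² group 18 if dose cohort means dose level.
- **That AML will never be estimated.** A cohort could by chance be all AML. The SAP section between 2.4.4 and 2.4.6 was not available, so a subgroup provision there cannot be excluded. SAP 3.3 also carries the qualifier if applicable.

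These points stand and limit the size of the finding. Two more are fair: the SAP does keep disease-specific analysis for Phase 2a, and individual AML response, death and follow-up data will be listed. It is also true that 7.2.2.1 names no AML progression category, so an AML PFS curve needs its event stated; AML OS does not have that problem. None of this supplies the analysis in 8.3.2.2 or explains its omission.

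**Conclusion.** The inconsistency is real. For Phase 1, the SAP text available replaces the protocol's by-disease PFS and OS at the MTD with a dose-cohort grouping, gives no reason, and plans no AML-specific estimate. The affected group is about 10 to 18 AML subjects at 400 mg/m² BID (at most 17 once the reported MDS responder at that dose is counted), plus the MDS/CMML subjects at that dose who do not count toward Phase 2a. This rests on 3 subjects in each of the other five cohorts and on to-date counts; up to 48 are planned, so the final numbers may differ.

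The consequence is an unanswered part of a secondary objective and, for PFS, curves that may combine different event definitions. SAP 2.4.2 plans no formal tests and the primary objective is safety, so no error rate or power is affected. It should be corrected, but it does not threaten the trial's main conclusions.

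**What to change.** In SAP 3.3, 4.1.5 and 4.2, add Kaplan-Meier PFS and OS with median and 90% confidence interval by disease (AML; MDS/CMML) for subjects treated at the MTD, as in protocol 8.3.2.2. State whether the 14-, 21- and 28-day schedules at 400 mg/m² BID are pooled for this, and name the event that counts as progression in AML. Align the synopsis with 8.3.2.2, making clear whether dose cohort and disease type are crossed. If the dose-cohort grouping is intended instead, record it in the SAP as a departure from the protocol, with the reason.

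An AML curve across all Phase 1 doses, labelled descriptive, is an optional addition. So is listing individual times in place of a median for very small cohorts. The cost is SAP and synopsis wording and a few extra tables and figures from data already collected.

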4.1.1. Subject Disposition

- Subject Disposition

4.1.2. Demographics and Baseline Characteristics

- Demographics and Baseline Characteristics (Ethnic, Race, Sex, Age at Study Entry, Weight, Height and ECOG)
- Baseline Disease Assessment - AML
- Baseline Disease Assessment - MDS/CMM

4.1.3. Prior and Concomitant Medication

- Summary of Prior Medications
- Summary of Concomitant Medications

4.1.4. Primary Efficacy Summaries

- Summary of Subject's Disease Response and 90% Confidence Intervals - AML
- Summary of Subject's Disease Response and 90% Confidence Intervals - MDS/CMM

4.1.5. Secondary Efficacy Summaries

- Summary of Subjects With Hematologic Improvement
- Progression Free Survival (PFS)
- Overall Survival (OS)

4.1.6. Safety Summaries

4.1.6.1. Study Drug Administration

- Summary of Study Drug Exposure

4.1.6.2. Adverse Events Summaries

- Summary of Treatment Emergent Adverse Events

- Treatment Emergent Adverse Events by System Organ Class and Preferred Term
- Treatment Emergent Adverse Events by Relationship to Study Drug
- Summary of Treatment Emergent Adverse Events by Severity
- Grade 3 and Grade 4 Treatment Emergent Adverse Events
- Drug-related Grade 3 and Grade 4 Treatment Emergent Adverse Events
- Treatment Emergent Adverse Events by System Organ Class and Preferred Term with at least 2% Incidence in any Group or overall

4.1.6.3. Laboratory Assessments

- Summary of Laboratory Assessments by Visit
- Change From Baseline in Laboratory Assessments by Visit
- Shift Table from Baseline to Most Extreme Post-Baseline Result by CTC Grade

4.1.6.4. Other Safety Summaries

- Summary of Vital Sign Results
- Change From Baseline in Vital Sign Results
- Change From Baseline in 12-Lead Electrocardiogram Results

4.2. Mock Graphs

- Progression Free Survival
- Overall Survival

4.3. Mock Listings

The following listings will be presented for subjects in Phase 1 dose escalation phase and for subjects in Phase 2a.

- Inclusion Criteria not Met
- Exclusion Criteria not Met
- Protocol Violations/Deviations/Exemptions
- Demographics
- End of Treatment
- End of Study
- Baseline Disease Assessment - AML
- Baseline Disease Assessment - MDS/CMMI
- Medical History
- Prior Cancer Surgery
- Physical Examination
- Prior Medications
- Concomitant Medications
- Study Drug Administration - Drug Dispensation
- Study Drug Administration – Patient Medication Diary
- Pharmacokinetic (PK) Sample Collection
- Pharmacodynamic (PD) Sample Collection

- Disease Response - AML
- Disease Response - MDS/CMML
- Bone Marrow Assessment (BMA)
- Treatment Emergent Adverse Events (TEAE)
- Serious Treatment Emergent Adverse Events
- Treatment Emergent Adverse Events Leading to Dose Adjustment, Temporary Interruption, and Permanent Discontinuation of Study Drug
- Treatment Emergent Adverse Events Leading to Permanent Discontinuation from Study
- Dose Limiting Toxicities
- Deaths
- Hematology
- Chemistry
- Urinalysis
- Pregnancy Test
- Vital Signs
- 12-lead Electrocardiogram
- Blood Transfusion
- Other Procedures
- Long Term Follow-up
